Appendix J. Inhibitors and Inducers of CYP3A

Inhibitors and inducers of CYP3A are defined as follows. A comprehensive list of inhibitors can be found at the following website: <http://medicine.iupui.edu/clinpharm/ddis/table.aspx>. The general categorization into strong, moderate, and weak inhibitors according to the website is displayed below. Refer to [Section 6.2.1](#) on instructions for concomitant use of CYP3A inhibitors and inducers with ibrutinib.

Inhibitors of CYP3A	Inducers of CYP3A
Strong inhibitors:	Carbamazepine
INDINAVIR	Efavirenz
NELFINAVIR	Nevirapine
RITONAVIR	Barbiturates
CLARITHROMYCIN	Glucocorticoids
ITRACONAZOLE	Modafinil
KETOCONAZOLE	Oxcarbazepine
NEFAZODONE	Phenobarbital
SAQUINAVIR	Phenytoin
SUBOXONE	Pioglitazone
TELITHROMYCIN	Rifabutin
Moderate inhibitors:	Rifampin
aprepitant	St. John's Wort
erythromycin	Troglitazone
diltiazem	
fluconazole	
grapefruit juice	
Seville orange juice	
verapamil	
Weak inhibitors:	
cimetidine	
All other inhibitors:	
amiodarone	
NOT azithromycin	
chloramphenicol	
boceprevir	
ciprofloxacin	
delaviridine	
diethyl-dithiocarbamate	
fluvoxamine	
gestodene	
imatinib	
mibefradil	
mifepristone	
norfloxacin	
norfluoxetine	
star fruit	
telaprevir	
troleandomycin	
voriconazole	

Source: <http://medicine.iupui.edu/clinpharm/ddis/table.aspx>.

Appendix K. Child-Pugh Score

Measure	1 point	2 points	3 points
Total bilirubin, $\mu\text{mol/L}$ (mg/dL)	<34 (<2)	34-50 (2-3)	>50 (>3)
Serum albumin, g/L (g/dL)	>35 (>3.5)	28-35 (2.8-3.5)	<28 (<2.8)
PT INR	<1.7	1.71-2.30	>2.30
Ascites	None	Mild	Moderate to Severe
Hepatic encephalopathy	None	Grade I-II (or suppressed with medication)	Grade III-IV (or refractory)

Points	Class
5-6	A
7-9	B
10-15	C

Source:

8.1	Visit Window for Analysis	20
8.2	SAS code to calculate Lee cGVHD symptom scale	20

ABBREVIATIONS

AE	adverse event
ALT	alanine aminotransferase
ANC	absolute neutrophil count
AST	aspartate aminotransferase
ATC	Anatomical Therapeutic Chemical
cGVHD	chronic graft versus host disease
CI	Confidence interval
CNS	central nervous system
CR	complete response
CRF	case report form
CTCAE v. 4.03	Common Terminology Criteria for Adverse Events version 4.03
CYP	cytochrome P450
DLT	dose limiting toxicity
DOR	Duration of response
eCcr	estimated creatinine clearance
ECG	Electrocardiogram
EDC	electronic data capture
FDA	Food and Drug Administration
FFS	failure free survival
ILD	Interstitial Lung Disease
IRRC	Independent Response Review Committee
MedDRA	Medical Dictionary for Regulatory Activities
MTD	maximum tolerated dose
NCI	National Cancer Institute
NIH	National Institutes of Health
PCYC	Pharmacyclics, LLC
PR	partial response
RP2D	recommended phase 2 dose
SAE	serious adverse event
SAP	Statistical Analysis Plan
SD	stable disease
SI	Système international d'unités
SMQ	Standardized MedDRA Query
SOC	System Organ Class
TEAE	Treatment emergent adverse event
ULN	upper limit of normal
WHO	World Health Organization

1. Introduction

Study PCYC-1129-CA is a Phase 1b/2 open-label study designed to evaluate the safety and efficacy of ibrutinib in subjects with steroid-dependent/refractory chronic graft versus host disease (cGVHD).

Phase 1b will begin with the evaluation of the 420 mg/day dose level of ibrutinib with the potential for subsequent dose reductions if dose limiting toxicities (DLTs) are detected. A modified 3+3+3 design will be used to determine a safe dose to carry forward to Phase 2 of the study (recommended Phase 2 dose [RP2D]).

Phase 2 will evaluate the efficacy of the RP2D of ibrutinib determined in Phase 1b. Subjects will be given ibrutinib continuously along with any pre-existing immunosuppressants for cGVHD and followed for signs of progression/resolution of cGVHD.

The purpose of this statistical analysis plan (SAP) is to provide a comprehensive description of the statistical analyses for efficacy and safety data that have been outlined within the protocol of Study PCYC-1129-CA (Amendment 2, dated 21 October 2015). The analyses will be executed by the Biometrics department of Pharmacyclics unless otherwise specified.

This plan does not cover the pharmacokinetic or pharmacodynamic analyses and biomarker analysis, which will be performed and reported by the separate groups of Pharmacyclics.

1.1 Study Objectives

1.1.1 Primary Objective

The primary objective of the Phase 1b part of the study is to evaluate the safety and tolerability of ibrutinib in subjects with steroid dependent/refractory cGVHD.

The primary objective of the Phase 2 part of the study is to evaluate the clinical efficacy of ibrutinib in steroid dependent/refractory cGVHD by measuring best overall cGVHD response (National Institutes of Health [NIH]-defined complete response and partial response).

1.1.2 Secondary Objectives

Phase 1b:

- To evaluate the clinical efficacy of ibrutinib in steroid dependent/refractory cGVHD by measuring:
 - Best overall cGVHD response (complete and partial response per NIH-defined cGVHD criteria)
 - Rate of sustained response for at least 5 months
 - Duration of response (DOR)
 - Corticosteroid requirement changes over time
 - Change in symptom burden measured by the Lee cGVHD Symptom Scale

Phase 2:

- To evaluate the clinical efficacy of ibrutinib in steroid dependent/refractory cGVHD by measuring:
 - Rate of sustained response for at least 5 months
 - Duration of response (DOR)
 - Corticosteroid requirement changes over time
 - Change in symptom burden measured by the Lee cGVHD Symptom Scale
- To evaluate the safety and tolerability of ibrutinib in steroid dependent/refractory cGVHD

1.1.3 Exploratory Objectives

The exploratory objective covered by this analysis plan is:

- To evaluate the clinical efficacy of ibrutinib by measuring failure free survival at 6 and 12 months

1.2 Study Design

The study will be conducted in two phases.

Phase 1b will begin with the evaluation of the safety of once daily dose (420 mg) ibrutinib with the potential for subsequent dose reductions if DLTs are detected. A modified 3+3+3 design will be used to determine a safe dose to carry forward to Phase 2 of the study. Once the RP2D is determined, Phase 2 will commence.

Phase 2 will evaluate the efficacy of the RP2D of ibrutinib determined in Phase 1b. Subjects will be given ibrutinib continuously along with their pre-existing immunosuppressant for cGVHD and followed for signs of progression/resolution of cGVHD. Approximately 34 subjects will be enrolled in Phase 2 to reach approximately 40 subjects (Phase 1b + Phase 2 subjects) treated at the RP2D.

1.3 Dosage and Administration

Three dose levels of ibrutinib may be tested: 140 mg/day, 280 mg/day, and 420 mg/day. The starting dose level is 420 mg/day and the dose level might be modified based on the DLTs.

The decision to proceed with a RP2D or to reduce the dose will be made in a Dose Level Review Meeting by the Sponsor in conjunction with the investigators after careful consideration of all available safety and laboratory information.

Following the establishment of the RP2D, the Phase 2 portion of the study will begin enrolling additional subjects.

1.4 Sample Size Justification

The Phase 1b part of the study is a modified 3+3+3 dose-finding design that is described in the protocol.

With a sample size of 40 subjects receiving the RP2D, and assuming an overall cGVHD response rate of 50%, the study is expected to have at least 90% power to show the efficacious treatment effect (the lower bound of 95% confidence interval [CI] of the response rate >25%).

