10.3. Sample Size Determination

With a sample size of 40 subjects and assuming an best overall cGVHD response rate of approximately 50%, it is expected to have at least 90% power to show the efficacious treatment effect (the lower bound of 95% CI of the response rate >0.25).

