10.4. Efficacy Analysis

Best overall cGVHD response rate and its 95% confidence interval will be calculated with the exact test for binomial distribution.

The secondary efficacy endpoint rate of sustained response for at least 5 months will be evaluated in the same manner as best overall cGVHD response rate.

The distribution (median and Kaplan-Meier curves) and estimates of DOR will be provided using Kaplan-Meier estimates for responders.

Other secondary endpoints, such as on corticosteroid requirement changes over time, change in symptom burden measured by the Lee cGVHD Symptom Scale will be summarized by descriptive statistics.

Exploratory endpoints will be summarized by descriptive statistics.

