5.1 Primary Endpoint

The primary efficacy endpoint is the best overall cGVHD response rate during the study based on investigator assessments. To assess the primary endpoint, the study used the 2005 NIH Consensus Panel Response criteria with two modifications based on the updated 2014 NIH Consensus Panel Response criteria: 1) “Not Evaluable” can be used for assessments where there is another non-cGVHD cause for the abnormalities documented and 2) a change in cGVHD organ score from 0 to 1 is no longer considered progression as is the case per the 2005 NIH cGVHD Response Criteria.

Best overall cGVHD response rate is defined as the proportion of subjects who achieve a NIH-defined complete response or partial response. The response rate and its 95% confidence interval (CI) will be calculated based on the exact test for binomial distribution. If the lower bound of the CI of the response rate is $\geq 25\%$, the primary efficacy objective is achieved.

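### The claimed power of at least 90% with 40 subjects does not hold: under the planned exact 95% interval it is 86.6%

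*SAP*

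**What the plan says.** SAP 1.4 sets out the design assumptions: "With a sample size of 40 subjects receiving the RP2D, and assuming an overall cGVHD response rate of 50" per cent, with success defined as "the lower bound of 95% confidence interval [CI] of the response rate >25" per cent. From these it concludes that "the study is expected to have at least 90% power to show the efficacious treatment effect". Protocol 10.3 has the same sample size and threshold, is slightly looser on the rate ("assuming an best overall cGVHD response rate of approximately 50" per cent), and reaches the same conclusion: "it is expected to have at least 90% power to show the efficacious treatment effect". Neither sample-size section says how the power was calculated.

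The interval itself is specified elsewhere. SAP 5.1 says the response rate and its 95% interval "will be calculated based on the exact test for binomial distribution". Protocol 10.4 says "Best overall cGVHD response rate and its 95% confidence interval will be calculated with the exact test for binomial distribution". The protocol synopsis also names an exact binomial interval. SAP 5.1 declares the primary objective met if the lower bound is at least 25%, and SAP 5.2 sets the study-wise type I error at two-sided 0.05.

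The sample size is a target rather than a fixed number: "Approximately 34 subjects will be enrolled in Phase 2 to reach approximately 40 subjects (Phase 1b + Phase 2 subjects) treated at the RP2D".

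**The concern.** A power statement should describe the test that will be run. Here the test is fully determined: exact two-sided 95% interval, threshold 25%, 40 subjects. Its power at 50% can therefore be calculated without any outside assumption, and it falls short of the stated figure.

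The figure matters because it is the only quantitative justification for the Phase 2 sample size. The primary endpoint also has a pass/fail rule, and SAP 5.2 allows the formal test of sustained response only if that rule is passed. The chance of reaching that second test is therefore overstated as well.

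**Working it through.** **Inputs.** n = 40, true rate p1 = 0.50 and threshold p0 = 0.25 (SAP 1.4, Protocol 10.3). Exact binomial 95% interval (SAP 5.1, Protocol 10.4, synopsis). Two-sided 0.05, so 0.025 in the lower tail (SAP 5.2).

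**Step 1: trying to reproduce the plan's figure.** The usual one-sample normal approximation, with the null variance in the critical value, is

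power = Φ{[(p1 − p0)√n − 1.96√(p0(1 − p0))] / √(p1(1 − p1))}

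= Φ{[0.25 × 6.3246 − 1.96 × 0.4330] / 0.5} = Φ(1.465) = 92.9%.

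With a continuity correction of 1/(2n) = 0.0125, the difference of 0.25 becomes 0.2375 and the result is 90.4%. An arcsine approximation gives 91.2%. With the alternative variance throughout, the normal approximation gives 88.5%. So a claim of at least 90% can be obtained from an approximate formula, which is its likely origin, but none of these formulas is the planned test.

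**Step 2: the success count under the exact rule.** The exact lower bound for r responders is the value p_L that solves P(X ≥ r | n = 40, p_L) = 0.025. It exceeds 25% only if P(X ≥ r | 40, 0.25) is below 0.025.

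| Responders of 40 | Exact lower bound | P(X ≥ r) at 25% | P(X ≥ r) at 50% | Success? |
|---|---|---|---|---|
| 15 | 22.73% | 5.44% | 95.97% | no |
| 16 | 24.86% | 2.62% | 92.31% | no |
| 17 | 27.04% | 1.16% | 86.59% | yes |
| 18 | 29.26% | 0.47% | 78.52% | yes |

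At least 17 responders are needed. No count has a lower bound of exactly 25%, so it makes no difference that SAP 1.4 asks for a bound above 25% and SAP 5.1 for a bound of at least 25%.

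**Step 3: power.** P(X ≥ 17 | 40, 0.50) = 0.8659. Type II error is 1 − 0.8659 = 0.1341. One-sided type I error at 25% is 0.0116.

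**Step 4: could another interval rescue the claim?** The Wald interval, with or without continuity correction, also needs 17 responders, so its power is 86.6% too. Wilson, Agresti–Coull, Jeffreys and mid-P intervals, and a one-sided 95% exact bound, all accept 16 responders and have power 92.3%. A cut-off of 16, however, has a type I error of 2.62%, above the 2.5% tail. With 40 subjects, therefore, no cut-off gives both a one-sided error of at most 2.5% and power of at least 90%.

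**Step 5: sample sizes near 40, exact rule.**

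| n | Responders needed | Power at 50% | One-sided type I error at 25% |
|---|---|---|---|
| 38 | 16 | 87.21% | 1.56% |
| 39 | 16 | 90.02% | 2.04% |
| 40 | 17 | 86.59% | 1.16% |
| 41 | 17 | 89.45% | 1.52% |
| 42 | 17 | 91.79% | 1.97% |
| 43 | 18 | 88.90% | 1.14% |
| 44 | 18 | 91.29% | 1.48% |

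Power rises and falls because the required count moves in whole steps. It stays at or above 90% for every n from 44 to 55, the largest size checked.

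**The case against.** The strongest reply is that the gap is small and comes mostly from discreteness. Sixteen responders miss the threshold by only 25.00 − 24.86 = 0.14 percentage points, and 39 subjects would reach 90.0% under the same rule. The plan speaks of approximately 40 subjects, and the protocol of approximately 50%. With 40 subjects, exact power is 89.1% at a true rate of 51% and 91.3% at 52%. Standard approximate formulas give 90.4% to 92.9%, and neither sample-size section names its method. Nothing in the analysis itself changes: endpoint, interval, threshold and type I error control are unaffected.

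Most of this is right. The figure is best described as inconsistent with the planned exact interval, not as inexplicable. The rule in SAP 5.1 is also complete without a printed responder count, so adding one is helpful rather than essential.

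The reply does not save the sentence, however. SAP 1.4 gives 40 subjects and 50% without qualification and says at least 90%. For the analysis both documents specify, that is untrue. Nor does approximate accrual support the claim, since power is below 90% at 38, 40, 41 and 43.

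**Conclusion.** The concern holds. Under the planned exact 95% interval, with 40 subjects and a true response rate of 50%, power is 86.6% against a stated minimum of 90%. That is a shortfall of 3.4 percentage points, with a type II error of 13.4%. The result uses only inputs given in the documents and assumes that exactly 40 subjects enter the primary analysis. The validity of the primary test is not in question: its one-sided type I error at 25% is 1.16%. The stated power is wrong as written and should be corrected, because it is the sole numerical basis for the sample size.

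**What to change.** Replace the power sentence in Protocol 10.3 and SAP 1.4 with wording such as: *With 40 subjects, the lower bound of the exact 95% confidence interval exceeds 25% if at least 17 respond; power at a true response rate of 50% is 87%, and the exact one-sided type I error at 25% is 1.2%.*

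As accrual is approximate, it would also help to list the required count and power for 39 to 42 subjects: 16 responders (90%), 17 (87%), 17 (89%) and 17 (92%). This is optional.

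The cost is one sentence per document, no extra patients and a slightly less favourable power figure. If the sponsor wants to keep the 90% claim, the alternative is to set a sample size that meets it under the exact rule: 42 (91.8%) or 44 (91.3%), which means two or four more subjects. Of these, 44 is the safer choice against modest over-accrual, because power falls to 88.9% at 43 but stays at or above 90% from 44 to 55.

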2.1 Subgroups

Subgroup analysis will be performed on the primary efficacy endpoint as well as TEAEs to assess the effect of the following factors (subgroups that have high levels of imbalance will be omitted):

1. Age (<65 vs. ≥65)
2. Gender (male vs. female).

3. General Analysis Considerations

3.1 Definitions

3.1.1 Study Day

Study day will be calculated in reference to the first dose of study drug. Study Day 1 corresponds to the date that the subject takes the first dose of study drug.

For dates before Study Day 1:

$$\text{Study Day } n = \text{Date of assessment/event} - \text{Date of Study Day 1}$$

For dates on or after Study Day 1:

$$\text{Study Day } n = \text{Date of assessment/event} - \text{Date of Study Day 1} + 1 \text{ day}$$

There will not be a Study Day 0.

3.1.2 Baseline Value

Unless otherwise specified, the baseline value is defined as the last valid measurement on or prior to the first dose of study drug

3.1.3 Postbaseline Value

The postbaseline value is defined as a measurement taken after the first dose of study drug.

For subjects with a valid, nonzero baseline value:

$$\text{Change from baseline} = \text{postbaseline value} - \text{baseline value};$$

$$\% \text{ change from baseline} = (\text{change from baseline}/\text{baseline}) * 100.$$

3.1.4 Duration of Treatment

Duration of treatment will be calculated from the date of the first dose of study drug to the date of the last dose of study drug, as follows:

$$\text{Duration of treatment} = \text{date of last dose of study drug} - \text{date of first dose of study drug} + 1 \text{ day}.$$

3.1.5 Time on Study

Time on Study will be calculated from the date of the first dose of study drug to the study exit date or the last known alive date if the subjects are still in the study, as follows:

$$\text{Time on Study} = \text{study exit date/last known alive date} - \text{date of first dose of study drug} + 1 \text{ day}.$$

For subjects who did not take the study drug, Time on Study is calculated from the date of enrollment to the study exit date.

3.1.6 Age

Age in years will be the subject age at the date of enrollment.

3.1.7 Dose Intensity

Dose intensity (mg/day) is defined as the ratio of total dose received in mg and treatment duration in days.

3.1.8 Relative Dose Intensity

Relative dose intensity (%) is defined as the percentage of total cumulative dose administered (mg) versus the total expected dose (mg). Total cumulative dose administered is the sum of daily dose taken over the whole study course; and total expected dose (mg) is the product of the duration of the treatment (day) and the protocol assigned daily dose. Relative dose intensity is calculated by total cumulative dose administered / total expected dose × 100%.

3.1.9 Estimate Creatinine Clearance Rate

Estimated creatinine clearance rate (eCcr) will be calculated using the Cockcroft-Gault formula

$$eCcr(mL/min) = \frac{(140 - Age) \times Weight (kg) \times [0.85 \text{ if Female}]}{72 \times Serum Creatinine (mg/dL)}$$

When serum creatinine is measured in $\mu\text{mol/L}$, the formula is

$$eCcr(mL/min) = \frac{(140 - Age) \times Weight (kg) \times C}{Serum Creatinine (\mu\text{mol/L})}$$

using a constant C of 1.23 for men and 1.04 for women.

In this calculation, if weight is not measured at the same visit as creatinine, the weight measured prior and closest to the creatinine collection time will be used.

3.1.10 Absolute neutrophil count

Absolute neutrophil count (ANC) is calculated by

$$ANC = (\% \text{ neutrophil} + \% \text{ bands}) \times \text{White blood cell} / 100$$

where white blood cell is in $10^9/L$.

3.2 Visit Windows

Visit windows have been given in the Time and Events Schedule of the protocol. For by-visit analysis, visit will be used to associate assessment with a scheduled visit and will be created in reference to the date of first dose of study drug to assign visit number based on evaluation date. Details for target date for each scheduled visit and time interval between scheduled visits are provided in 20.

- If more than one assessment falls into a given visit window, the non-missing one closest to the target date will be used. If two assessments are equally close to the target day, the earlier assessment will be used.

3.3 Missing and Incomplete Data

In order to achieve the goal of a well-conducted clinical study according to Good Clinical Practice, every effort will be made to collect all data. However, despite best efforts, it may be inevitable that some data may be missing or incomplete. In the subject data listing, the available data, including partial data will be presented as they are recorded on the case report forms (CRFs).

Time-to-event or duration-of-event endpoints will be based on the study day rather than visit number or visit label. No imputation of missing values will be performed for efficacy data unless otherwise specified.

No imputation of missing values for safety data will be performed unless otherwise specified.

3.3.1 Missing Date of the Last Dose of Study drug

When the date of the last dose of the study drug is missing for a subject in the All Treated Population, all efforts should be made to obtain the date from the Investigator. If it is still missing after all efforts are made, the information will not be imputed. The subject might be excluded from some analyses due to the missing information.

3.3.2 Missing Date Information for Safety Endpoints

For missing or partial start and end dates for AEs, medical history, prior therapy and concomitant medication, no imputation will be performed. However, a conservative approach will be taken when performing the related analyses. If the available information is not enough to judge whether an event or a therapy duration has overlapped with study treatment duration, events reported on AE pages will be taken as treatment emergent AEs, events reported on medical history page will be treated as prior medical condition, prior or concomitant therapy will be considered as continuing therapy which started prior to first study treatment.

However, an intermediate imputation of partial dates may be taken in order to calculate the study day for AEs, medical history, prior therapy and concomitant medications. This is just for estimation of the timing of events relative to the study course. All missing or partial dates should remain the same values as they were recorded on the CRFs. The intermediate imputation rules are:

If only day is missing, then the 15th of that month will be used.

If only year is present, then June 30th will be used.

If such imputed date for prior therapies or initial diagnosis is on or after the date of the first dose of study drug, then date of the first dose – 1 day will be used. If such imputed date for the start or end of subsequent therapies is before date of last dose of study drug, then date of last dose of study drug +1 day will be assumed. If an imputed start date of prior or subsequent therapy is after the end date, the end date will be used. If an imputed end date of prior or subsequent therapy is before its start date, the start date will be used.

If an imputed AE start date is in the same month and year as the first dose date of study drug but on an earlier date, the first dose date will be used. If an imputed AE start date is

in the same month and year as the date of 30 days post the last dose of study drug but on a later date, the date of 30 days post the last dose will be used. If an imputed AE start date is after the AE end date, the AE end date will be used.

If the imputed date is for an AE end date and is after the death date, then the death date will be used, or if the imputed AE end date is before the AE start date, then the AE start date will be used.

The average daily use of corticosteroid will be used to evaluate the treatment effect. All efforts should be made to obtain the date from the Investigator. If it is still missing after all efforts are made, the information might be imputed with a conservative approach. If a date was missed in the middle of other corticosteroid uses, we might need to fill this dose to the whole gap between the records with imputation.

